225 *World Health Organization Quality of Life (WHOQOL)-BREF* (68), composed of 26 items rated on
226 a 5-point Likert scale assessing four domains: physical health (7 items on mobility, daily activities,
227 functional capacity, energy, pain, and sleep), psychological health (6 items on self-image, negative
228 thoughts, positive attitudes, self-esteem, mentality, learning ability, memory concentration, religion,
229 and the mental status), social relationships (3 items on personal relationships, social support, and sex
230 life), and environmental health (8 items related to financial resources, safety, health, and social
231 services); it also contains QOL and general health items. The scores (range 25 to 130) are transformed
232 linearly to a 0–100-scale.

233

234 Moreover, *adherence* will be measured through indicators such as the percentage of visited pages or the
235 number of accesses.

236 *Acceptability* will be assessed by registering the participants' attrition rates and – for the experimental
237 group only - by the use of the *System Usability Scale* (SUS)(69) composed of 10 statements scored
238 on a 5-point Likert scale (from 1 = strongly disagree to 5 = strongly agree). The final score range from
239 0 to 100, with a score above 68 indicating the absence of usability problems.

240

241 **Procedure**

242 Those interested in taking part in the program will be directed to the RinasciMENTE website
243 (<https://www.iterapi.se/sites/rinascimente/login>) where they will find the written (online) consent,
244 and after the acceptance of this, to each participant will be sent a document with information on the
245 aims and requirements of the study.

246 They will be first asked to complete the GHQ-12 self-report questionnaires. Then, during the
247 following 5 days, they will choose a time slot to be contacted for a clinical semi-structured interview

248 lasting about 45 minutes, led by a certified clinical psychotherapist not involved in the study who will
249 further assess the individual's eligibility to take part in the study. Additional information about the
250 study and the randomization procedure will be also given to all respondents.

251 Next, the inclusion of each participant in the study and modules comprising the program will be
252 discussed in a group by the professional who will conduct the interview and the research investigators

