281 communicating the update of the new material on the platform. Participants who will not access the
282 material or that will not complete the suggested tasks and exercises will receive a weekly reminder
283 containing a brief encouraging message every Monday.

284 At the end of the program (after two months – T1), participants in both conditions will be asked to
285 fill in the baseline questionnaires again. Then, the experimental group will be also assessed after 6-
286 and 12 months from the term of the treatment (T2 and T3) (Figure 1).

287 **Statistical analysis**

288 Statistical analyses were performed using SPSS software ver. 24.0 (76).

289 First, preliminary analyses will be performed to test the assumptions of both univariate and
290 multivariate normality: if (strong) violations will be detected, robust methods or data transformation
291 will be applied. Dropouts will be excluded from the study.

292 A missing values analysis will be run to see if the values are Missing Completely at Random
293 (MCAR), or if there is some pattern among missing data. If there are no patterns detected, then
294 pairwise or listwise deletion will be done to deal with missing data. However, if the missing values
295 analysis detects a pattern, then imputation will be done.

296

297 The demographic characteristics will be reported as means and standard deviations for continuous
298 variables, and frequencies and percentages for categorical variables.

299 The chi-square statistic will be used to test the association between treatment groups and socio-
300 demographic and variables (i.e., age, gender, education, civil status, job), and correlation analysis
301 will be used to test the association between quantitative variables.
302 The outcomes will be compared in the two treatment conditions using an Intention-To-Treat (ITT)
303 approach. The significance level will be set at 5%.
304 A repeated-measures ANOVA will be used to determine whether there are any between and within
305 groups differences in the selected outcomes from baseline to treatment termination. , Then repeated-
306 measures within group ANOVA will test outcome differences over time baseline, end of treatment,
307 6- and 12-month follow-up) in the experimental group only (. Corrected effect sizes (Cohen's *d*) and
308 significance at 95% confidence interval (95% CI) will be calculated for both between-group and

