309 within-group differences, while for the total effect will be calculated the Cohen's *f*.

310 **DISCUSSION**

311 To help and mitigate the impact of the COVID-19 pandemic on selected psychological parameters,
312 the objective of this study is to evaluate the effectiveness of an Internet-based self-help intervention
313 based on CBT principles and techniques, in reducing the level of stress, anxiety, depression, and fear
314 of COVID-19, while increasing emotions self-regulation and perceived self-efficacy of Italians both
315 living in the country and abroad. .

316 The online modality was chosen due to the current multiple barriers for face-to-face psychological
317 interventions (i.e., mobility), and its largely acknowledged advantages, including greater flexibility
318 or the possibility to reach rural or low-income population (77), and Italians living outside the country
319 who look for psychological support in their language. Also, the self-help approach to therapy will be
320 employed to further improve access to treatments and empower users to strengthen their self-
321 management ability, while putting less strain on therapeutic resources (78) than conventional
322 treatments do.

323

324 **Expected results**

325 The results of this RCT will provide evidence for the feasibility and effectiveness of the
326 RinasciMENTE program in supporting the emotional well-being of the persons. Specifically, people
327 are expected to show reduced levels of stress, anxiety, depression, and fear of COVID-19, as well as
328 improved emotion regulation strategies, and self-efficacy. They are also expected to acquire the skills
329 necessary to deal with the psychological consequences of social isolation during and after the
330 COVID-19 outbreak.

331 Still, among the weaknesses of this study, it must be anticipated possible lack of internet access and
332 digital literacy skills of some people.

333 Non-digital natives (i.e., older people) might, indeed, experience difficulties in the use of digital tools,
334 and social isolation can pose additional challenges to their usage (i.e., chaotic home environments,
335 limited privacy, or unreliable internet connection) (79).

336 The use of online intervention might also prevent effective controlling of confounding variables (i.e.
337 environmental factors) that might impact treatment outcomes (80).

338 The results from this study will help to detect and address any usability problem, as Internet-based

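### A SUS score above 68 cannot be read as showing that users had no usability problems, and the score may come from completers only

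*Combined protocol and SAP*

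**What the plan says.** The last paragraphs of Methods, Measures, deal with adherence and acceptability. Adherence is described by platform use, such as pages visited or number of accesses, with no threshold. Acceptability "will be assessed by registering the participants' attrition rates", also without a threshold, and, in the experimental group only, by the SUS. The SUS is "composed of 10 statements scored" from 1 to 5, with a final score between 0 and 100, "with a score above 68 indicating the absence of usability problems". No scoring formula or time point is given for it. The plan does not say whether 68 is applied to each user or to the group mean, or what is done when a SUS form is missing.

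Three other places bear on this. The hypotheses at the end of the Background include feasibility in the primary hypothesis, with no criterion attached. The Statistical analysis section states "Dropouts will be excluded from the study" and later gives an intention-to-treat approach for comparing outcomes between the two conditions. The Discussion (Expected results) says "The results from this study will help to detect and address any usability problem, as Internet-based" programmes may suit the general population, and predicts that dropout may be higher than in face-to-face therapy.

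**The concern.** A total adds good and bad ratings together, so a good total can coexist with bad ratings on individual statements. A group mean adds a second layer of averaging over users. Reading either as proof that there were no problems goes further than the score allows, and fits poorly with the stated hope of finding any usability problem. The Discussion itself expects some users, such as older people, to struggle with digital tools. A minority of that kind is what a mean conceals.

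There is also the question of who answers. People who stop because the platform did not work for them are the most informative respondents on usability. If they are left out, the reported score is likely to be too favourable. Followed as written, the plan could lead the report to state that usability problems were absent when a sizeable minority had them.

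**Working it through.** **Inputs from Methods, Measures:** 10 statements; answers 1 to 5, so four steps from worst to best; final score 0 to 100; cut-off above 68. **From Sample size calculation:** 64 participants per group. **Assumption:** equal weights, since the plan gives no scoring formula.

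**Reproducing the stated range.** Let each statement contribute 0 (worst) to 4 (best) after adjusting for direction. Score = sum × 100 / (10 × 4) = sum × 2.5. All worst gives 0 and all best gives 40 × 2.5 = 100, as stated. Each statement is worth 0 to 10 points. Totals move in steps of 2.5, so above 68 means 70 or more for an individual. The value 68 itself cannot be derived from the documents.

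**Individual reading.** Highest total with *w* worst answers and all others best = (10 − *w*) × 10:

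- *w* = 1: 90, above 68
- *w* = 2: 80, above 68
- *w* = 3: 70, above 68
- *w* = 4: 60, below 68

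The case *w* = 3 is a limit. If one of the other seven answers is one step below best, the total is 67.5; if all seven are, it is 7 × 3 × 2.5 = 52.5. The case *w* = 2 has more room: four of the other eight can be one step below best and the total is still (4 × 4 + 4 × 3) × 2.5 = 70. Four answers one step above worst with six best also give (4 × 1 + 6 × 4) × 2.5 = 70.

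**Group-mean reading (assumed; all 64 answer).** With 25 users at 50 and 39 at 80: (25 × 50 + 39 × 80) / 64 = 4370 / 64 = 68.3, above 68. So 25 / 64 = 39% of users could be well below the cut-off while the mean passes. With 26 at 50 the mean is (1300 + 3040) / 64 = 67.8 and fails.

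**Leaving out those who stop (all figures assumed).** The documents give no dropout rate and no SUS values. Suppose completers average 72 and leavers average between 40 and 55. All-user mean = 72 × (1 − *d*) + leavers' mean × *d*:

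- *d* = 10%: 68.8 to 70.3
- *d* = 20%: 65.6 to 68.6
- *d* = 30%: 50.4 + 12 = 62.4 to 50.4 + 16.5 = 66.9

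A completers-only analysis reports 72 throughout. Under these assumptions the conclusion stays the same at 10%, may change at 20%, and changes at 30%.

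**The case against.** The strongest reply is that this is one phrase about a measure that is neither a primary nor a secondary outcome, that nothing in the efficacy analysis depends on it, and that the examples are extreme or assumed. Much of that stands, and several stronger readings should be set aside.

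- A reader might infer that any user with three worst answers passes. That is not so; it needs the best answer to all seven other statements. But the plan's wording claims absence of problems, so possible counterexamples are enough to defeat it, and those with one or two worst answers are less extreme.
- A reader might infer that 68 is the trial's feasibility success rule. The plan files the SUS under acceptability and never ties 68 to the primary hypothesis. Feasibility has no stated criterion at all, which is a separate gap.
- A reader might infer that the Discussion relies on the SUS to detect problems. It refers to the study's results in general; adherence and attrition data are results too.
- A reader might infer that people who leave are ignored. They are counted in attrition, the other half of acceptability. Attrition does not show, however, whether usability made them leave.
- A reader might see a fault in giving the SUS to one arm only. Waiting-list participants have no access to the treatment until the experimental group has finished, so they have nothing to rate during the comparison period.
- A reader might infer that 68 is a poor benchmark. The documents do not allow that to be judged, and the point does not need it.

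It can also be said that the intention-to-treat sentence overrides the exclusion of dropouts. The two do conflict for the outcomes. But that sentence concerns comparisons between the arms, and the SUS has none, so it does not settle who contributes to the SUS. Equally, the plan does not say that leavers are not sent the SUS; completers-only data is a possibility left open by the text.

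**Conclusion.** The point holds as a defect of interpretation and reporting. A SUS above 68 does not show that usability problems are absent, whether 68 is applied to individuals (up to three worst answers possible) or to the mean of 64 users (25 at 50 possible). This rests on equal weighting, which reproduces the stated 0 to 100 range. The plan should also say which use is intended.

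The selection concern holds in a smaller form. The text permits a completers-only SUS and the plan expects considerable dropout, but the size of any effect cannot be obtained from the documents. The range of 62.4 to 66.9 at 30% leaving, against 72 in completers, shows only that the conclusion could change. Nothing here touches the comparison of the OQ-45 or the secondary outcomes between arms.

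**What to change.** In Methods, Measures, delete the statement that a score above 68 means there are no usability problems. In its place, and in Statistical analysis, specify:

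- the mean SUS with its 95% CI;
- the share of users at or below 68;
- for each of the ten statements, the share of unfavourable answers;
- that the SUS is offered at T1 to every experimental participant who logged in, including those who stopped, with the number answering reported out of those allocated.

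Offering it at T1 gives all users one common time point. Tying the request to missed weekly reminders would also catch active users who merely skipped a task, and would mix early with end-of-programme ratings.

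The cost is one more automated 10-item request to people who stopped, who will probably respond at a low rate, and one extra table. A low response does not remove the selection problem, but reporting the denominator makes it visible. The efficacy analysis does not change.

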281 communicating the update of the new material on the platform. Participants who will not access the
282 material or that will not complete the suggested tasks and exercises will receive a weekly reminder
283 containing a brief encouraging message every Monday.

284 At the end of the program (after two months – T1), participants in both conditions will be asked to
285 fill in the baseline questionnaires again. Then, the experimental group will be also assessed after 6-
286 and 12 months from the term of the treatment (T2 and T3) (Figure 1).

287 **Statistical analysis**

288 Statistical analyses were performed using SPSS software ver. 24.0 (76).

289 First, preliminary analyses will be performed to test the assumptions of both univariate and
290 multivariate normality: if (strong) violations will be detected, robust methods or data transformation
291 will be applied. Dropouts will be excluded from the study.

292 A missing values analysis will be run to see if the values are Missing Completely at Random
293 (MCAR), or if there is some pattern among missing data. If there are no patterns detected, then
294 pairwise or listwise deletion will be done to deal with missing data. However, if the missing values
295 analysis detects a pattern, then imputation will be done.

296

297 The demographic characteristics will be reported as means and standard deviations for continuous
298 variables, and frequencies and percentages for categorical variables.

299 The chi-square statistic will be used to test the association between treatment groups and socio-
300 demographic and variables (i.e., age, gender, education, civil status, job), and correlation analysis
301 will be used to test the association between quantitative variables.
302 The outcomes will be compared in the two treatment conditions using an Intention-To-Treat (ITT)
303 approach. The significance level will be set at 5%.
304 A repeated-measures ANOVA will be used to determine whether there are any between and within
305 groups differences in the selected outcomes from baseline to treatment termination. , Then repeated-
306 measures within group ANOVA will test outcome differences over time baseline, end of treatment,
307 6- and 12-month follow-up) in the experimental group only (. Corrected effect sizes (Cohen's *d*) and
308 significance at 95% confidence interval (95% CI) will be calculated for both between-group and
309 within-group differences, while for the total effect will be calculated the Cohen's *f*.

310 **DISCUSSION**

311 To help and mitigate the impact of the COVID-19 pandemic on selected psychological parameters,
312 the objective of this study is to evaluate the effectiveness of an Internet-based self-help intervention
313 based on CBT principles and techniques, in reducing the level of stress, anxiety, depression, and fear
314 of COVID-19, while increasing emotions self-regulation and perceived self-efficacy of Italians both
315 living in the country and abroad. .

316 The online modality was chosen due to the current multiple barriers for face-to-face psychological
317 interventions (i.e., mobility), and its largely acknowledged advantages, including greater flexibility
318 or the possibility to reach rural or low-income population (77), and Italians living outside the country
319 who look for psychological support in their language. Also, the self-help approach to therapy will be
320 employed to further improve access to treatments and empower users to strengthen their self-
321 management ability, while putting less strain on therapeutic resources (78) than conventional
322 treatments do.

323

324 **Expected results**

325 The results of this RCT will provide evidence for the feasibility and effectiveness of the
326 RinasciMENTE program in supporting the emotional well-being of the persons. Specifically, people
327 are expected to show reduced levels of stress, anxiety, depression, and fear of COVID-19, as well as
328 improved emotion regulation strategies, and self-efficacy. They are also expected to acquire the skills
329 necessary to deal with the psychological consequences of social isolation during and after the
330 COVID-19 outbreak.

331 Still, among the weaknesses of this study, it must be anticipated possible lack of internet access and
332 digital literacy skills of some people.

333 Non-digital natives (i.e., older people) might, indeed, experience difficulties in the use of digital tools,
334 and social isolation can pose additional challenges to their usage (i.e., chaotic home environments,
335 limited privacy, or unreliable internet connection) (79).

336 The use of online intervention might also prevent effective controlling of confounding variables (i.e.
337 environmental factors) that might impact treatment outcomes (80).

338 The results from this study will help to detect and address any usability problem, as Internet-based
339 interventions, due to their characteristics and format, might be a suitable and feasible solution to
340 mitigate the psychological impact of the virus outbreak and its related containment measures on the
341 mental health status of the general population across the lifespan. Moreover, the findings will
342 contribute to the further adaption of the self-help CBT programs.

343 In line with previous research findings, it is possible to predict that dropout rates may be higher with
344 web-based interventions than in traditional face-to-face therapy (80), especially when self-help
345 programs are used. To overcome this problem, participants in the study will receive a weekly
346 reminder and motivational messages to access the online material. A positive relationship between
347 each respondent and their referral therapist will be also supported, and while on the one hand, the
348 professional remains available in case of need, the subject takes responsibility over the course of the

349 treatment. The learning process is emphasized, so to help the person improve self-management skills
350 and strategies to deal with their emotional problems.

351 Furthermore, the online format brings with it the advantage of allowing us to also support the
352 population of Italians abroad, of which the literature does not report any in-depth analysis.
353 RinascIMENTE, therefore, represents the first attempt to provide online psychological support to the
354 segment of the Italian population abroad.

355 **CONCLUSION**

356 Since the beginning of the COVID-19 pandemic, studies demonstrated a significant clinical and
357 statistically decrease in mental health across populations worldwide. This burden is expected to
358 continue in the aftermath making high demand for timely and pragmatic psychological interventions
359 tailored to the unique and immediate needs of the general public. Preventive measures, fear of being
360 infected, and financial losses give a reason for the implementation and use of digital self-help
361 programs based on CBT principles and techniques – which might offer a range of self-management
362 strategies to cope with emotional difficulties, besides reducing the cost of the health care system (81).

363 **DECLARATION**

364 ***Ethics approval and consent to participate***

365 The study protocol and informed consent to participate were approved by the Research Ethics

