145 score ≥ 15 on the GHQ and show moderate levels of symptoms at the clinical interview will be
146 included in the study.

147 Participants will be excluded from the program if: (A) presenting visual, hearing, or cognitive
148 impairments that will prevent them from receiving and following the intervention; (B) suffering from
149 severe psychiatric disorders according to the Diagnostic and Statistical Manual of Mental Disorders
150 (DSM 5) (52); (C) lacking basic computer skills or internet access.

151 Respondents will not be excluded if already receiving psychopharmacological therapy or
152 psychological-psychotherapeutic support.

153 **Sample size calculation**

154 The minimum sample size required to conduct this study was calculated using an a priori sample size
155 calculator (G*Power 3.1.9.2 software) for *F* tests (53-55). Participants were randomly divided into
156 two groups: (A) iCBT self-help and (B) waiting list control. Moreover, participants will be measured
157 in 3 moments: (1) before the intervention, (2) at the end of intervention (two months later), and (3)
158 after 12 months from treatment termination. Due to the novelty of the study from which to derive
159 realistic estimates of effect sizes, the partial η^2 was set a priori to assume a value of 0.02 – small
160 effect size (56, 57) – which provides a Cohen's *f* value of 0.143. Moreover, the type I error (α) rate
161 was set at 0.05 (two-sided) and the Power ($1 - \beta$) was set at 0.95, and the a priori correlation between
162 repeated measures was set at 0.50, according to general guidelines (56). Lastly, the non-sphericity
163 correction was set to 1. Results showed that there is a 95% chance of correctly rejecting the null
164 hypothesis of no significant effect of the interaction with 128 participants in total (64 for each group).

165 **Randomization and blinding**

166 The random randomization scheme will be generated using the Web site Randomization.com (58).
167 Allocation concealment will be ensured by the program generating an anonymous code for each
168 participant that will be associated with the randomization sequence. Due to the nature of the
169 intervention, the treatment group allocation cannot be concealed from the participants, nor the
170 research team and assessor of outcomes. Participants will be assigned to one of two conditions within
171 2 working days from their baseline assessment (Figure 1).

172

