173 *** PLEASE INSERT Figure 1: Flow chart of the RinasciMENTE study

174 **Measures**

175 *Demographic and clinical information.* Information about age, gender, education, civil status, weight, and
176 high - used to calculate the Body Mass Index (BMI, kg/m²) in presence of dysfunctional eating behaviors
177 - will be self-reported online at baseline. Subjects will be also asked to provide information about the
178 country where they are currently living, their work situation (before and after the COVID-19 pandemic),
179 and the personal experience they made of both COVID-19 pandemic and related preventive measures.
180 The Italian version of the following psychological measures will be also collected at baseline (T0),
181 treatment termination after 2 months (T1), at 6-month (T2), and 12-month (T3) follow-up in the
182 experimental condition only). Please see Figure 2 for a detailed project timeline.

183 *** INSERT GANTT Figure 2: Gant of the RinasciMENTE study

184 Primary outcome:

185 *Outcome Questionnaire (OQ-45)* (59) composed by 45 items rated on a 5-point Likert scale (0 = Never –
186 4 = Almost always) assessing the treatment progresses across 3 different domains: Symptom Distress (SD
187 – 25 items: 2, 3, 5, 6, 8, 9, 10, 11, 13, 15, 22, 23, 24, 25, 27, 29, 31, 33, 34, 35, 36, 40, 41, 42 and 45),
188 Interpersonal Relations (IR – 11 items: 1, 7, 16, 17, 18, 19, 20, 26, 30, 37 and 43), and Social Role (SR –
189 9 items: 4, 12, 14, 21, 28, 32, 38, 39 and 44). The OQ-45 total score is calculated by summing the score of
190 the three subscales. Total score (range 0 to 180) is calculated by the sum of the items.

191 *Secondary outcomes:*

192 *Perceived stress scale* (PSS) (60), composed of 10 items rated on a 5-point Likert scale (from 0 = never to
193 4 = very often) assessing the degree to which situations in one's life are appraised as stressful. PSS scores
194 are obtained by reversing responses (i.e., 0 = 4, 1 = 3, 2 = 2, 3 = 1 and 4 = 0) to the four positively stated
195 items (items 4, 5, 7, and 8) and then summing across all scale items. The total score (range 0 to 40) is
196 calculated by the sum of the items.

197 *Emotional regulation questionnaire (ERQ)* (61), composed of 10 items rated on a 7-point Likert scale
198 (from 1 = strongly disagree to 7 = strongly agree) assessing respondents' tendency to regulate their

199 emotions in two ways: Cognitive Reappraisal (items 1, 3, 5, 7, 8, and 10) and Expressive Suppression

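### The T0–T1 repeated-measures ANOVA is less precise than a baseline-adjusted model, and the undefined normality rule leaves the primary method open in a trial whose team knows the allocation

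*Combined protocol and SAP*

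**What the plan says.** All references are to the combined protocol and SAP.

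- **Normality rule (Statistical analysis).** The section opens with "First, preliminary analyses will be performed to test the assumptions of both univariate and" and continues "multivariate normality: if (strong) violations will be detected, robust methods or data transformation". It names no test, cut-off, robust method, transformation, order of preference or masked review. The rule covers all outcomes and does not exempt the primary one, the OQ-45, which Measures defines by "the three subscales. Total score (range 0 to 180) is calculated by the sum of the items".
- **Between-arm test (Statistical analysis).** "A repeated-measures ANOVA will be used to determine whether there are any between and within" groups, from T0 to T1, at the 5% level. T0 is a level of the time factor, not a covariate. Measures and Procedure give the waiting-list arm only T0 and T1; the 6- and 12-month assessments are for the experimental arm alone.
- **Masking (Randomization and blinding).** "intervention, the treatment group allocation cannot be concealed from the participants, nor the" "research team and assessor of outcomes".
- **Design figures (Sample size calculation).** Partial eta-squared 0.02, f = 0.143, correlation 0.50, non-sphericity correction 1, alpha 0.05, power 0.95, three measurements, group-by-time interaction; N = 128 (64 per arm).
- **Reporting (Statistical analysis).** Cohen's d with 95% confidence intervals, and Cohen's f. The scale to be used after a transformation is not stated.

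**The concern.** Two weaknesses meet in the primary comparison.

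The first is efficiency. The trial collects the T0 OQ-45 in both arms. A two-point repeated-measures ANOVA uses it by subtraction, which is not the most precise way unless the T0–T1 correlation is close to 1.

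The second is pre-specification. What counts as a *strong* violation is left to the analyst, and so is what replaces the ANOVA. Two competent analysts following the text could report different primary p-values, and nothing in the plan separates the choice of method from sight of results by arm. If a transformation is chosen, the trial no longer estimates a mean difference in OQ-45 points, so the quantity being estimated would depend on the data.

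At stake are the credibility of a primary p-value near 5%, the interpretability of the effect estimate, and precision that costs nothing to recover.

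**Working it through.** **1. Reproduce the plan's N.** For the interaction, λ = f²·N·m/(1 − ρ), df₁ = m − 1 and df₂ = (N − 2)(m − 1), with f = √(0.02/0.98) = 0.143, ρ = 0.50 and two arms.

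- m = 3 measurements: 95% power needs N = 128 (power 95.1%). The stated figure reproduces.
- m = 2, the T0–T1 comparison actually possible between arms: N = 128 gives about 89% power, and 95% power needs N = 162.

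**2. Express the two-point test as a change-score test.** I take the interaction as the test of interest, as the sample-size paragraph does. With two arms and two times its F is the square of the t for T1 − T0. In units of a common SD, the change has variance 2(1 − ρ). Equating noncentralities at m = 2, Δ²·N/[8(1 − ρ)] = 2f²N/(1 − ρ), so Δ = 4f = 4 × 0.143 = 0.572 SD at T1.

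**3. Compare with baseline adjustment.** The residual variance given T0 is 1 − ρ². The ratio is (1 − ρ²)/[2(1 − ρ)] = (1 + ρ)/2. At ρ = 0.50 this is 0.75/1.00, a 25% reduction, equivalent to 128/0.75 ≈ 171 participants analysed by change score.

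With 64 per arm:

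- change score: noncentrality 0.572/(1.000 × √(2/64)) = 3.24, power about 89%;
- adjusted model: noncentrality 0.572/(0.866 × √(2/64)) = 3.74, power about 96%. N for 95% power falls from 162 to 122.

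**4. Vary the correlation** (only 0.50 is in the plan; the others are assumed; Δ = 0.572 SD, N = 128).

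| ρ | Variance ratio | Power, change | Power, adjusted |
|---|---|---|---|
| 0.3 | 0.65 | 0.77 | 0.92 |
| 0.5 | 0.75 | 0.89 | 0.96 |
| 0.6 | 0.80 | 0.95 | 0.98 |
| 0.8 | 0.90 | >0.99 | >0.99 |

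For smaller assumed effects at ρ = 0.50, power goes from 0.80 to 0.90 (0.5 SD) and from 0.61 to 0.74 (0.4 SD).

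**5. Simulate the normality rule under no effect.** 5,000 trials of 64 per arm, ρ = 0.5, scores rounded and limited to 0–180. The documents give no OQ-45 mean, SD or shape, so the three shapes (normal, moderate skew, strong skew) are assumed, as are the options (untransformed, log, square root, rank, trimmed). Monte Carlo standard error is about 0.3 points at 5% and 0.4 points at 9%.

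| Procedure | Type I error across shapes |
|---|---|
| Fixed untransformed test | 5.0%–5.4% |
| Fixed baseline-adjusted model | 4.8%–5.3% |
| Mechanical switch to one set method | 4.7%–5.8% |
| Smaller p of untransformed and rank | 6.0%–6.7% |
| Smaller p of untransformed and log | 6.3%–7.8% |
| Smallest p of all five | 7.8%–9.3% |
| Smallest of five, only after any-cell Shapiro–Wilk p < 0.05 | 5.4%–9.3% |

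The lowest value in the last row is for normal scores, where the trigger seldom fires.

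**6. Show what the missing trigger definition does.** Under moderate skew the switch fires in 99.6% of trials if any cell with Shapiro–Wilk p < 0.05 counts, in 49% if absolute skewness above 1 is required, and in 22% if Shapiro–Wilk is applied to change scores.

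**The case against.** The strongest reply is that the rule does no harm in itself. Applied mechanically it leaves the error rate where the fixed test has it. The 6%–9% figures describe an analyst who runs several methods and keeps the best p-value, which the plan does not prescribe. That stands. A reader might infer that the rule as written raises the false-positive rate; the documents support only that it leaves room for this.

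A reader might also infer that the method is chosen after inspecting unmasked results. The open design makes that possible, but no section says who runs the check, when, or with arm results in view; the text places it first, as a preliminary step. The same caution applies to how often the switch would fire: a rate near 100% reflects one assumed shape and one assumed criterion.

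Three further points stand. Repeated-measures ANOVA is valid under randomisation and does use T0; it uses it inefficiently. Cohen's d is unitless, so the scale argument concerns the mean difference, and a robust method may keep the raw scale. Baseline adjustment is an efficiency gain separate from the normality rule.

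None of this supplies the missing trigger, the missing fallback or the lost precision.

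**Conclusion.** The point holds as two linked, moderate weaknesses. Neither invalidates the trial.

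**Precision.** At the plan's correlation of 0.50, the T0–T1 ANOVA carries one third more error variance than the adjusted model (1/0.75); equivalently, adjustment saves 25%, or 10%–35% for assumed correlations of 0.8 down to 0.3. At f = 0.143 with two time points and N = 128, power is about 89% against about 96%. This assumes equal variance at T0 and T1, f carried unchanged from three measurements to two (hence 0.572 SD), and no dropout.

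**Pre-specification.** The primary method is not determined by the text. The type I error is about 5%–6% under a mechanical switch and about 6%–9% if the most favourable option is picked. Both are simulation ranges that depend on assumed shapes and option sets, not properties of the plan. A transformation would also move the mean difference off the OQ-45 scale.

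**What to change.** In Statistical analysis, fix the primary analysis as the T1 OQ-45 total on its raw 0–180 scale, in a linear model with arm and T0 OQ-45 and heteroscedasticity-robust standard errors, whatever the normality checks show. Report the adjusted mean difference in OQ-45 points with its 95% confidence interval. Use the same model for each secondary score. List any transformed or rank analyses by name as sensitivity analyses.

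The cost is wording and one model specification; T0 and T1 are already collected in both arms. The small downside is that the Sample size calculation paragraph, built on a three-measurement interaction F test, should be restated for this model. Under the assumptions above, 95% power needs 122, so 128 covers it with only 128 − 122 = 6 participants to spare for loss.

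This does not settle the data-dependent choice between deletion and imputation, or the exclusion of dropouts, in the same section. Those need their own resolution.
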